5.5 Duration of Follow Up

Upon discontinuation of therapy in patients without documented disease progression, every effort should be made to continue monitoring patients' disease status by radiologic imaging either at the investigative site or locally. Imaging will be collected and evaluated per RECIST 1.1.

- Year 1 Post-Treatment: Imaging will be performed Q 3 months (± 14 days) or as clinically indicated for the first year post-completion of treatment.
- Years 2 and 3 Post-Treatment: Imaging will be performed Q 6 months (± 1 month) or as clinically indicated during years 2 and 3 post-treatment.
- If the study remains open, imaging will be performed annually once patient has completed 3 years of follow up for disease assessment.
- Collection of standard of care disease assessments will continue until progression, start of a new anticancer therapy, death or end of study, whichever occurs first.

Patients removed from protocol therapy for unacceptable AE(s) will be followed for resolution or stabilization of the AE or 1 year, whichever is longer, in addition to following for disease assessments.

Disease assessments will be collected until (1) the start of new anticancer treatment, (2) documented disease progression, (3) death, or (4) the end of the study, whichever occurs first.

After progression or start of a new anticancer treatment, patients will be followed for survival ([Section 5.1.1](#)). Time to death will be chronicled for all patients.

5.6 Criteria for Removal from Study

Patients will be removed from study when any of the applicable criteria, including progressive disease, withdrawal, or inability to follow study protocol as listed in [Section 5.4](#). The reason for study removal and the date the patient was removed must be documented in the Case Report Form.

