- Years 2 and 3 Post-Treatment: Imaging will be performed Q 6 months (\pm 1 month) or as clinically indicated during years 2 and 3 post-treatment.
- If the study remains open, imaging will be performed annually or as clinically indicated once patient has completed 3 years of follow up for disease assessment.
- Collection of standard of care disease assessments will continue until progression, start of a new anticancer therapy, death or end of study, whichever occurs first.

Survival Follow-Up Phone Contacts (every 12 weeks \pm 1 week)

Begin survival follow-up phone contacts after discontinuing MK-3475 due to disease progression or start of a new anticancer therapy (initiate 12 weeks \pm 1 week following the Post-Treatment Safety Follow-Up Visit). Survival follow-up will continue until death or the end of the study, whichever occurs first.

5.1.2 ***Other Agent(s): N/A***

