- Live vaccines within 30 days prior to the first dose of trial treatment and while participating in the trial. Examples of live vaccines include, but are not limited to, the following: measles, mumps, rubella, chicken pox, yellow fever, rabies, BCG, and typhoid (oral) vaccine. Seasonal influenza vaccines for injection are generally killed virus vaccines and are allowed; however, intranasal influenza vaccines (e.g. Flu-Mist[®]) are live attenuated vaccines, and are not allowed.
- Glucocorticoids for any purpose other than to modulate symptoms from an event of suspected immunologic etiology. The use of physiologic doses of corticosteroids may be

approved after consultation with the Protocol P.I.

Patients who, in the assessment by the investigator, require the use of any of the aforementioned treatments for clinical management should be removed from the trial. Patients may receive other medications that the investigator deems to be medically necessary.

The Exclusion Criteria describes other medications which are prohibited in this trial. There are no prohibited therapies during the Post-Treatment Follow-up Phase.

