5.4 Duration of Therapy

In the absence of treatment delays due to adverse event(s), treatment may continue for up to 2 years or until one of the following criteria applies:

- Disease progression warranting alternative systemic therapy,
- Intercurrent illness that prevents further administration of treatment,
- Patient decides to withdraw from the study.
- General or specific changes in the patient's condition render the patient unacceptable for further treatment in the judgment of the investigator.
- In patients with documented disease progression, treatment with MK-3475 can continue until one of the above occurs or until there is an increase in tumor burden of 25% or more following initial confirmation of progression.
- Unacceptable adverse event(s), including:
 - Any Grade 2 drug-related uveitis or eye pain or blurred vision that does not respond to topical therapy and does not improve to Grade 1 severity within the re-treatment period OR requires systemic treatment.
 - Grade 3 drug-related autoimmune or inflammatory event including uveitis, pneumonitis, diarrhea, colitis, neurologic adverse events, hypersensitivity reaction, or infusion reaction of any duration requires discontinuation.
 - Any Grade 3 or 4 drug-related laboratory imbalance or electrolyte abnormality, not associated with underlying organ pathology and that do not require treatment except for electrolyte replacements do not require treatment discontinuation, with the following exceptions with approval of the Principal Investigator:
 - Hypophysitis or pan-hypopituitarism any grade should discontinue treatment.
 - Grade 4 amylase or lipase abnormalities that are not associated with DM, associated liver or gall bladder inflammation clinical manifestations of pancreatitis and which decrease to <Grade 4 within 1 week of onset may stay

on study.

- Any drug-related liver function test (LFT) abnormality that meets the following criteria requires discontinuation: Grade 3 AST or ALT ($>5 \times$ ULN) and total bilirubin $>3 \times$ ULN.
- Grade 3 drug-related thrombocytopenia >7 days or associated with bleeding requires discontinuation.
- Any patient requiring systemic steroid or other immunosuppressive treatment.

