5.11 Beginning and End of the Trial

The study begins when the first patient signs the informed consent. The end of the study may be designated as the time point when all patients have discontinued the study or are a minimum of 6 months post-completion of study medication administration. At this point, a database lock of the trial may occur to allow the analysis of the study data. (Prior to the final database lock at the end of the study, interim database locks may occur to allow interim analysis of study data). Any remaining patients may continue to receive study medication and be seen by the investigator per usual standard of care for this patient population. In addition, the investigator will be expected to monitor for and report any SAEs, or pregnancies, as detailed in [Section 7](#). The patient is considered on study until such time that he/she meets any of the discontinuation criteria and written notification is given to the Protocol P.I./CITN.

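### Sections 5.6 and 5.3.1, and less clearly 5.11, take patients off the study where other sections require continued follow-up; read literally, they put OS, and to a lesser degree 16-month PFS, at risk of informative censoring

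*Combined protocol and SAP*

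**What the plan says.** **Text that takes patients off the study**

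- Section 5.6: "Patients will be removed from study when any of the applicable criteria, including progressive disease, withdrawal, or inability to follow study protocol", with the criteria taken from Section 5.4. The reason for and date of study removal must be entered in the CRF. Section 5.4 is headed Duration of Therapy. It lists progression warranting other systemic therapy, intercurrent illness, patient withdrawal and a long entry beginning "Unacceptable adverse event(s), including".
- Section 5.3.1: patients who "require the use of any of the aforementioned treatments for clinical management should be removed from the trial". The list covers other anticancer therapy, radiation (with an exception by consultation) and glucocorticoids outside the permitted uses.
- Section 5.11: "The patient is considered on study until such time that he/she meets any of the discontinuation criteria and written notification is given" to the protocol PI or CITN. The criteria are not defined there.

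**Text that keeps the same patients in follow-up**

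- Section 5: after confirmed progression, patients who stop therapy are still followed for survival.
- Section 5.1.1: patients stopping without progression continue imaging, and for survival contacts, "Survival follow-up will continue until death or the end of the study, whichever occurs first".
- Section 5.5: imaging continues to progression, new anticancer therapy, death or study end, and "Time to death will be chronicled for all patients".
- Calendar footnotes o and r repeat both duties.

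**Analysis rules (13.5.1.2)**

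PFS without an event is censored at the last disease assessment, and OS at the date last known alive. One PFS sensitivity analysis counts patients who stopped treatment or began new therapy without documented progression or death as progressed. OS has no such analysis.

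**The concern.** Leaving treatment and leaving the study are different events, and Kaplan-Meier estimates of PFS and OS depend on keeping them apart. Section 5.6 converts a list of the first kind into a list of the second kind and asks the site to date it. A coordinator who reads 5.6 or 5.3.1 alone has a written instruction to close the patient's record at the point where prognosis changes. Censoring at that point is informative, and the usual direction of the bias is upward.

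PFS and OS are both named secondary endpoints, and 16-month PFS is to be set against a historical 5%. Section 13 says no separate SAP will be issued, so the protocol is the only place where the conflict can be settled.

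**Working it through.** The conflict itself is textual and the plan gives no figure to reproduce. The arithmetic below only sizes what a literal reading could do.

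**1. Which reason for removal touches which endpoint**

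| Reason | Removal text | Follow-up text | Endpoint exposed on a literal reading |
|---|---|---|---|
| Documented progression | 5.6, by name | Section 5; 5.5; footnote r | OS only, because progression is already the PFS event |
| Toxicity, intercurrent illness | 5.6, through 5.4 | 5.1.1; 5.5; footnote o | PFS and OS |
| Non-permitted steroid or radiation | 5.3.1 | 5.1.1; 5.5; footnote o | PFS and OS |
| New anticancer therapy | 5.3.1 | 5.5 itself ends imaging here; survival follow-up continues | OS; the PFS censoring comes from 5.5 |

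Section 5.11 names none of these reasons and adds written notification as a second condition, so it supports the conflict only weakly. Section 5.6 also sits uneasily with Sections 5 and 5.8, which allow treatment to continue after confirmed progression. Those passages need reconciling too, and I take no view on the clinical rule.

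**2. OS if follow-up ended at progression**

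Assume exponential times. Let h be the total PFS hazard, f the share of PFS events that are deaths without progression, d = f·h, p = h − d, and q the death hazard after progression.

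- True OS(t) = e^(−ht) + [p/(h − q)]·[e^(−qt) − e^(−ht)]
- Kaplan-Meier OS when patients are censored at progression = e^(−dt)

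Take a median PFS of 9 months, a median post-progression survival of 6.3 months and f = 0.10, all assumed. The 6.3 is a rough anchor: the Section 2.1.7 chemotherapy data give a median OS of 9.5 months and a median PFS of 98.5 days, about 3.2 months, and 9.5 − 3.2 = 6.3.

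- h = 0.693/9 = 0.0770; d = 0.0077; p = 0.0693; q = 0.693/6.3 = 0.1100
- True OS(16) = 0.2916 + (−2.10)(0.1720 − 0.2916) = 0.543
- Censored at progression: e^(−0.0077 × 16) = 0.884

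Over median PFS of 3.2, 9 or 18 months, post-progression medians of 4, 6.3 or 12 months, and f of 5% or 10%, true 16-month OS runs from 17% to 81%. The censored estimate runs from 71% to 97%. This supposes that every progressor is dropped, so it is an upper limit on the harm.

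**3. PFS if some patients are removed before progression**

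Assume exponential PFS with 16-month value S and λ = −ln(S)/16. A fraction g of those who would progress before 16 months is removed 2 months earlier. Approximately,

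Kaplan-Meier PFS(16) ≈ S^k, with k = (1 − g)/[1 − g(1 − e^(−2λ))].

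- S = 0.40: λ = 0.0573 and 1 − e^(−2λ) = 0.108. For g = 10%, k = 0.910 and the result is 43.4%. For g = 20%, k = 0.818 and the result is 47.3%.
- S = 0.30: 33.3% and 37.1%.

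Simulation with 50 patients per replicate agrees: 43.6% and 47.5% from 40%, and 33.5% and 36.8% from 30%. The values of g and the 2-month lead are invented for illustration.

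**4. The only early toxicity stops the protocol reports**

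Two of the first 26 patients stopped for drug-related events after one dose. The protocol does not say that they were lost to follow-up. If both were censored at baseline and the estimate from the remaining 24 were 50%, the bounds would be 0.50 × 24/26 = 46.2% and (0.50 × 24 + 2)/26 = 53.8%.

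**The case against.** A reader might infer something stronger: that the plan itself creates informative censoring of both PFS and OS for progression, toxicity and prohibited therapy alike. The documents do not support that.

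- **The follow-up duty is specific and repeated.** Section 5.1.1 describes patients discontinued from the study for a drug-related event and then requires imaging of those same patients, so the protocol uses the phrase loosely. Section 5.3.1 adds "There are no prohibited therapies during the Post-Treatment Follow-up Phase", which presupposes a phase after treatment stops. Off treatment is the natural reading of the whole.
- **Progression cannot censor PFS**, since it is the event.
- **Imaging stops at new anticancer therapy because of 5.5.** Rewording 5.6 would not change that.
- **Steroids and radiation are not blanket triggers.** Section 5.3.1 permits steroids for suspected immune events, and radiation to a symptomatic solitary lesion or the brain may be allowed after consultation.
- **The PFS sensitivity analysis addresses much of the PFS risk.** In the scenarios of step 3 it returns the true 16-month value when removal is taken as the treatment-stop date.
- **ORR is largely protected.** Section 13.13.2 keeps all eligible treated patients and counts unknown response as failure.

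All of this stands, and it makes the bias conditional on how a site reads the text. It does not remove the conflict, because no passage gives precedence. Nor does the sensitivity analysis recover missing scans or deaths. As worded, it would also count as progressed a complete responder who stops treatment as the protocol allows, so it bounds the PFS result without correcting it.

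**Conclusion.** The point holds as a contradiction in operative text with a conditional consequence. Sections 5.6 and 5.3.1, and less clearly 5.11, cannot be followed literally together with Sections 5, 5.1.1 and 5.5 and footnotes o and r.

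OS is the more exposed endpoint. Under the assumed models, full literal application at progression would turn a 16-month OS of 54% into an estimate of 88%, and no planned OS analysis would reveal it. The PFS exposure is smaller: about 3 to 7 percentage points in an illustration whose removal rates have no source in the protocol. Shifts of that size do not change the comparison with 5%.

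Nothing in the documents shows that any patient was lost this way. The change should be made because it is cheap and the OS risk is material. The primary endpoint does not hinge on it.

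**What to change.** - In 5.6 and 5.3.1, replace removal from the study or trial with discontinuation from study treatment. State that these patients remain on study for disease assessment and survival as in 5.5.
- In 5.11, define the discontinuation criteria as off-study events only: death, withdrawal of consent to follow-up, loss to follow-up, or study end.
- Record the off-treatment and off-study dates, each with its reason, in separate CRF fields.
- Reconcile the progression wording of 5.6 with Sections 5 and 5.8. Leave every treatment-stopping criterion as it is.
- Enrolment is complete, so query existing study-removal entries and seek vital status and later scans where consent allows.

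The cost is amendment wording, one added CRF date field with its reason, and a limited round of queries. No visit is added, because 5.5 already plans the follow-up.

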5.6.1 Patient Replacement Strategy

Patients that have received only 1 dose of MK-3475 will not be replaced unless therapy was stopped due to toxicity.

5.7 Criteria to Resume Treatment

For non-autoimmune or inflammatory events, patients may resume treatment with study drug when the drug-related AE(s) resolve to Grade ≤ 1 or baseline value, with the following exceptions:

- Patients may resume treatment in the presence of Grade 2 fatigue.
- Patients with baseline Grade 1 AST/ALT or total bilirubin who require dose delays for reasons other than a 2-grade shift in AST/ALT or total bilirubin may resume treatment in the presence of Grade 2 AST/ALT OR total bilirubin.
- Patients with combined Grade 2 AST/ALT AND total bilirubin values meeting study parameters outlined in Section 5.4 should have treatment permanently discontinued.
- Non-drug-related toxicity including hepatic, pulmonary toxicity, diarrhea, or colitis, must have resolved to baseline before treatment is resumed.
- Drug-related endocrinopathies (not including drug-related adrenal insufficiency or hypophysitis) adequately controlled with only physiologic hormone replacement may resume treatment after replacement correction and clinically stable regimen.

If the criteria to resume treatment are met, the patient should restart treatment no sooner than the next scheduled time point per protocol. However, if the treatment is delayed past the next scheduled time point per protocol, the treatment should resume at the earliest convenient point that is within the 12 week delay period.

If treatment is delayed >12 weeks, the patient must be permanently discontinued from study therapy, except as specified in [Section 5.4](#) (Duration of Therapy).

5.8 Treatment Beyond Progression

Immunotherapeutic agents such as MK-3475 may produce antitumor effects by potentiating endogenous cancer-specific immune responses. The response patterns seen with such an approach may extend beyond the typical time course of responses seen with cytotoxic agents, and can manifest as a clinical response after an initial increase in tumor burden or even the appearance of new lesions.

If radiologic imaging shows progressive disease (PD), tumor assessment will be repeated by the site approximately 4 weeks later in order to confirm PD with the option of continuing treatment per below while awaiting radiologic confirmation of progression. If repeat imaging shows a reduction in the tumor burden compared to the initial scan demonstrating PD, treatment may be continued as per treatment calendar. If repeat imaging confirms PD, patients will be discontinued from study therapy, if alternate therapy is needed. Alternatively, patients who are otherwise clinically stable may be continued on MK-3475, per investigator discretion. Even if the patient remains otherwise stable, MK-3475 treatment will be discontinued if tumor burden increases by 25% or more following initial confirmation of progression.

In determining whether or not the tumor burden has increased or decreased, investigators should consider all target lesions as well as non-target lesions. The decision to continue study treatment after the first evidence of disease progression, and upon confirmation of PD, determined by radiologic imaging, is at the Investigator's discretion based on the clinical status of the patient as described in the table below.

Patients may receive study treatment while waiting for confirmation of PD and if continuing MK-3475 after confirmation of PD, if they are otherwise clinically stable as defined by the following criteria:

- Absence of clinical symptoms or signs indicating disease clinically significant disease progression
- ECOG performance status ≤ 1
Absence of rapid disease progression or threat to vital organs or critical anatomical sites (e.g., spinal cord compression) requiring urgent alternative medical intervention

	Clinically Stable		Clinically Unstable	
	Imaging	Treatment	Imaging	Treatment
1 st radiologic evidence of PD	Repeat imaging at approximately 4 weeks to confirm PD	May continue study treatment at the Investigator's discretion while awaiting confirmatory scan	Repeat imaging at approximately 4 weeks to confirm PD if possible	Discontinue treatment
Repeat scan	No additional	Discontinue	No additional	N/A

confirms PD	imaging required if treatment discontinued. If treatment continues, regularly scheduled imaging assessments continue every 9 or 12 weeks	treatment or continue treatment at the Investigator's discretion	imaging required	
Repeat scan shows SD, PR, or CR	Continue regularly scheduled imaging assessments every 9 or 12 weeks	Continue study treatment at the Investigator's discretion	Continue regularly scheduled imaging assessments every 9 or 12 weeks	May restart study treatment if condition has improved and/or clinically stable per Investigator's discretion
Tumor imaging will be assessed first at week 13, then every 9 weeks (63±3 days) during the first year of treatment. Subsequently, tumor imaging will be performed every 12 weeks (84 ±7 days).				

5.9 Discontinuation of Treatment Following Complete Response

Discontinuation of treatment may be considered for patients who have attained a confirmed complete response (CR) that have been treated for at least 24 weeks with MK-3475 and had at least two treatments with MK-3475 beyond the date when the initial CR was declared.

5.10 Retreatment with MK-3475 of patients with recurrence

Some patients may be eligible to receive MK-3475 in the Retreatment Period of this study if the study remains open and the patient meets the following conditions:

- Patient stopped initial treatment with MK-3475 after attaining an investigator-determined confirmed CR on MK-3475 therapy
 - Was treated for at least 24 weeks with MK-3475 before discontinuing therapy;
 - Received at least 2 treatments with MK-3475 beyond the date when the initial CR was declared; or
- Patient with confirmed SD or PR completed 2 years of MK-3475 study treatment.
- Experienced an investigator-determined confirmed radiographic disease progression after stopping their initial treatment with MK-3475
- Did not receive any anticancer treatment since the last dose of MK-3475

- Meets safety parameters in Eligibility/Exclusion Criteria outlined in [Section 3.1](#) and [3.2](#)

Note: Patients that relapse on MK-3475 and are eligible for retreatment are encouraged to be retreated, however, the final decision is up to the treating physician and the patient.

Patients who restart treatment will be retreated at the same dose and frequency as when they last received MK-3475.

5.11 Beginning and End of the Trial

The study begins when the first patient signs the informed consent. The end of the study may be designated as the time point when all patients have discontinued the study or are a minimum of 6 months post-completion of study medication administration. At this point, a database lock of the trial may occur to allow the analysis of the study data. (Prior to the final database lock at the end of the study, interim database locks may occur to allow interim analysis of study data). Any remaining patients may continue to receive study medication and be seen by the investigator per usual standard of care for this patient population. In addition, the investigator will be expected to monitor for and report any SAEs, or pregnancies, as detailed in [Section 7](#). The patient is considered on study until such time that he/she meets any of the discontinuation criteria and written notification is given to the Protocol P.I./CITN.

